7.2.2 Cellular Immunity Testing

To assess cellular immunity flow cytometry will be performed in peripheral blood mononuclear cells (PBMC) in a subset of participants to examine SARS-CoV-2 specific B and T-cell lymphocyte subsets prior to and following booster dosage of vaccine. Based upon baseline serologic levels individuals will be categorized as non-responders (who never attained convalescent level of anti-RBD) or those with waning antibody levels. In total approximately 50 participants at University Health Network and Sunnybrook Health Sciences Centre are anticipated to have samples drawn for this sub-study. PBMC will be collected prior to third dose booster, 1 month, and 6 months following booster dose. ELISpot (enzyme-linked immunospot) assays to evaluate SARS-CoV-2 specific cellular immunity will be harmonized with protocols with other CITF studies.

7.2.3 Evaluation for COVID-19 Infection

To avoid potential contamination of the study result by participants who develop COVID-19 during the study period, natural COVID-19 infection will be detected by serologic assessments with Anti-NP which has a sensitivity of approximately 79%. Participants who present with any signs or symptoms of COVID-19 will be swabbed with SARS-CoV-2 nasopharyngeal swabs as per current screening protocols. Participants who develop COVID-19 infection during the study will be excluded from the analysis.

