3.2 Secondary Objectives/Outcomes

1. Measurement of Anti-Spike, Anti-NP antibodies, and SARS-CoV-2 specific neutralization at 1 month (30 days) following third dose of vaccine.
2. Determine the effect of a third dose of COVID-19 vaccine on humoral immune response in hemodialysis patients who did not attain convalescent serum levels or exhibiting declining antibody levels below convalescent serum levels of Anti-RBD through measurement of Anti-Spike, Anti-RBD, and Anti-NP antibodies at 3 months, 6 months and 12 months following booster dosage.
3. In a subset of participants, assess cellular immunity through flow cytometry on PBMC and single-cell RNA sequencing prior to, one month, and 6 months following vaccine booster.
4. Evaluate adverse events related to third dose of vaccine through a questionnaire within 48 hours to 14 days and 30 days following third vaccine dose.
5. Differences in COVID-19 infections, symptomatic COVID-19 infections, hospitalization, and death between study groups.

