10.5 Final Analysis Plan

The final analysis plan will be developed by the biostatistician in conjunction with the Principal Investigator. The targeted sample size for this study will be 300 due to feasibility, although a lower number are estimated to be required based upon sample size calculations above, and the final sample size may be adjusted by the Principal Investigator dependent upon study recruitment. If the final sample size is adjusted, a Clinical Trial Amendment will be filed. The proportion of patients receiving BNT162b2 and mRNA-1273 will be reported.

Quantitative Anti-SARS-CoV-2 IgG targeting the spike protein, RBD, nucleocapsid, and neutralizing antibodies will be reported at each time point as relative levels. Descriptive statistics will be used to describe baseline characteristics of patients in all four arms of the study. Mean

and median timing between first, second, and third (booster) vaccine dosage will be reported. Differences in the cell-mediated immunity as measured through flow cytometry on PBMC will be exploratory. Pre-specified clinical outcomes will include COVID-19 infections, COVID-19 related hospitalizations, and death.

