10.5.1 Statistical Analysis of the Primary Outcome

An intention-to-treat analysis will be followed for the primary outcome. The primary outcome will be the proportion of patients who attain convalescent serum levels of Anti-RBD at 1 month (30 days) following third dose of vaccine. Two Chi-Squared test or Fisher's exact test will be used, one for those who received first two doses of *BNT162b2* and the second for those who received *mRNA-1273* for the first two doses. This study is powered to determine differences between the use of *mRNA-1273* vaccine and *BNT162b2* vaccine as the booster dose on the primary outcome based on a clinically significant difference of 25% as described above in the sample size considerations. An adjusted analysis with logistic regression modelling will be performed if imbalance in baseline characteristics is found to between study groups following stratified randomization. Individuals who develop new COVID-19 infection as determined by a positive Anti-NP serologic test or positive SARS-CoV-2 RT-PCR nasopharyngeal swab during the study will be excluded from analysis of the primary outcome.

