10.5.2 Statistical Analysis of Secondary Outcomes

Secondary outcomes will include the proportion of patients who attain Anti-Spike median convalescent serum at 1 month (30 days) following third dose of vaccine. Differences in relative antibody levels (Anti-Spike and Anti-RBD) and neutralizing antibodies between study groups will be assessed through the Mann-Whitney test. The relative levels of antibodies will be tracked

longitudinally for each patient permitting analysis of SARS-CoV-2 antibody kinetics following vaccination and will be assessed through a mixed-effects repeated measures model with random intercepts and fixed covariates following log transformation of relative ratios, which will be exploratory. Differences in serial levels in relative antibody levels will be compared through a mixed effects model as above. Similar to the primary outcome, those with a new positive Anti-NP serologic test or COVID-19 nasopharyngeal swab during the study will be excluded from analysis. An intention to treat analysis will be followed, although an exploratory per protocol analysis may also be reported.

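### The rule excluding participants infected during the study is not limited to immune-response endpoints, so read literally it sets the COVID-19 components of secondary objective 5 to zero in every group

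*Combined protocol and SAP*

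**What the plan says.** Two places remove infected participants without naming the endpoints concerned.

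- Section 7.2.3: "Participants who develop COVID-19 infection during the study will be excluded from the analysis". The reason given is "To avoid potential contamination of the study result by participants who develop COVID-19 during the study period".
- Section 10.5.2, on the analysis of secondary outcomes: "those with a new positive Anti-NP serologic test or COVID-19 nasopharyngeal swab during the study will be excluded from analysis". The same paragraph continues: "An intention to treat analysis will be followed, although an exploratory per protocol analysis may also be reported".

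Section 10.5.1 has a parallel rule with a stated scope: participants with new infection "during the study will be excluded from analysis of the primary outcome".

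Two places make infection and its consequences an outcome.

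- Section 3.2, objective 5 (also in the Protocol Summary): "Differences in COVID-19 infections, symptomatic COVID-19 infections, hospitalization, and death between study groups".
- Section 10.5: "Pre-specified clinical outcomes will include COVID-19 infections, COVID-19 related hospitalizations, and death".

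Exclusion criterion 4 in Section 5.3 also concerns new infection after enrolment, although its list is introduced as applying at baseline. Section 5.5.1 places randomization at enrolment, so such an infection can be post-randomization. Under Section 7.3, infected participants resume the study after quarantine.

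**The concern.** The tests that detect the outcome, a new positive Anti-NP or a positive swab, are the same tests that remove the participant. No sentence exempts the clinical outcomes, and none gives them a separate analysis set.

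Two things are at stake. First, an analyst who follows the text would tabulate no COVID-19 infection in any group, in a population that Section 2.1 describes as being at high risk. Second, the exclusion acts on participants and not on events. Someone with a detected infection also leaves the counts of all-cause hospitalization and death. Those comparisons are then made among people selected by something that happened after randomization and that the booster itself may influence.

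If the point stays open, the analysis set for objective 5 may be chosen late. Participants are unblinded at about 30 days (Section 5.5.2), while these events accrue to month 12.

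**Working it through.** **The plan's own figure.** No rate, power or sample size is stated for objective 5. The only stated size is for the primary outcome (Section 10.2): 25% versus 50%, 80% power, two-sided alpha 0.05. With pooled variance and no continuity correction,

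n = [1.96·√(2·0.375·0.625) + 0.8416·√(0.25·0.75 + 0.50·0.50)]² / 0.25² = (1.342 + 0.557)² / 0.0625 ≈ 57.7,

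which rounds up to 58 per group, and 4 × 58 = 232. This matches the plan, and nothing below changes it.

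**Objective 5 under the literal rule.**

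| Component | What the exclusion removes | What is left to compare |
|---|---|---|
| Infection | Every infection detected by Anti-NP or swab | 0 in every group |
| Symptomatic infection | Every one so detected | 0 in every group |
| COVID-19 related hospitalization (Section 10.5 wording) | Every one following a detected infection | 0 in every group |
| Hospitalization, cause not restricted (Section 3.2 wording) | All events in participants with a detected infection | Events in participants with none |
| Death | All deaths in participants with a detected infection | Deaths in participants with none |

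The first three rows do not depend on the true infection rates, so no between-group difference can be estimated from them. The last two rows keep events.

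**Illustration with assumed values.** The documents give no expected infection rate. Assume 300 / 2 = 150 participants per booster and a true infection risk r of 5%, 10% or 20% over follow-up. Take detection by Anti-NP alone at the 79% sensitivity given in Section 7.2.3. Swabs would raise detection, so the undetected column is an upper value.

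| r | Infections, 150·r | Detected and excluded, ×0.79 | Undetected, ×0.21 | Participants left | Infections countable |
|---|---|---|---|---|---|
| 5% | 7.5 | 5.925 | 1.575 | 144.075 | 0 |
| 10% | 15 | 11.85 | 3.15 | 138.15 | 0 |
| 20% | 30 | 23.7 | 6.3 | 126.3 | 0 |

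Undetected infections stay in the analysis set but cannot be counted. If one booster group had a 10% risk and the other 5%, the expected 15 and 7.5 infections would both be analysed as 0. The groups left for all-cause hospitalization and death would be 138.15 and 144.075 participants. The exclusion is then unequal between arms for a reason tied to the treatment effect.

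**Intention to treat.** Removing participants for an event after randomization does not fit the intention-to-treat statement made in the same paragraph of Section 10.5.2.

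**The case against.** The strongest reply is that the rule was meant for serology only.

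- The stated reason is contamination. Natural infection can contaminate an antibody reading, but not a count of infections.
- Section 10.5.2 names only antibody and neutralization outcomes, and its exclusion sentence is introduced by analogy with the primary outcome, which is serologic.
- Section 10.5 lists the clinical outcomes with no exclusion attached.
- Section 7.2.4 plans sequencing of breakthrough infections, and Section 7.3 brings infected participants back into the study. Neither suggests a wish to disregard them.
- Section 4.1 explains that infection and hospitalization were not made primary because incidence was low, and no power is claimed for them. Section 10.5 leaves the final analysis plan to be developed, so the point can still be settled.

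As a reading of intent this is probably right, and it means the point is a contradiction in drafting, with no loss of data. It does not remove the contradiction. Section 10.5.1 limits its exclusion to the primary outcome; Sections 7.2.3 and 10.5.2 contain no such limit, and 10.5.2 is the section headed as the analysis of secondary outcomes. If events are few, there is more reason not to discard them.

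A reader might go further and infer that objective 5 is wholly empty. The documents do not support that. Death is not restricted to COVID-19 in either list, and Section 3.2 does not restrict hospitalization, so events in participants without detected infection remain. A reader might also size the loss from the Ontario dialysis hospitalization and case-fatality figures in Section 2.1. Those describe infected chronic dialysis patients, whereas this trial also enrols non-dialysis CKD and gives everyone a third dose. Without an expected infection rate they do not size anything here.

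**Conclusion.** The contradiction is real and limited in reach. Applied as written, detected infections, symptomatic infections and the COVID-19 hospitalizations or deaths that follow them are zero in every group by construction. The remaining hospitalizations and deaths are conditioned on a post-randomization event, against the plan's own intention-to-treat statement.

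The zero result needs no numerical assumption, only a literal reading of Sections 7.2.3 and 10.5.2. The illustrative counts rest on assumed infection risks of 5% to 20%, 150 participants per booster and detection by Anti-NP alone.

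The primary outcome and the sample size of 58 per group, 232 in total with a target of 300, are unaffected by this point. It should be corrected before the clinical outcomes are analysed, but it does not threaten the trial's main conclusion.

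**What to change.** 1. In Sections 7.2.3 and 10.5.2, limit the infection exclusion to the antibody and cellular endpoints.
2. Add to Section 10.5.2 that infection, symptomatic infection, hospitalization and death are analysed in all randomized participants by assigned booster, with infected participants counted as events.
3. Reword exclusion criterion 4 in Section 5.3 so that an infection after randomization does not remove a participant from this analysis.
4. Reconcile hospitalization as worded in Section 3.2 with the COVID-19 related hospitalizations of Section 10.5, and state which is the outcome or that both are reported.
5. Name the data source for each component to month 12. Anti-NP at 1, 3, 6 and 12 months and swabs for symptoms are already planned. Adverse-event collection stops 30 days after dosing (Section 8.5), and the schedule has no entry for hospitalization or death. The provincial tracking in Sections 7.4 and 8.7 is described mainly for dialysis patients, and Section 5.7 foresees survival data after withdrawal where possible.

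Items 1 to 4 cost only a few sentences. Item 5 is also mainly wording where the trial or provincial systems already hold the data. For non-dialysis participants the sponsor should confirm that a source exists, because the documents do not clearly describe one. No sample-size figure and no part of the primary analysis changes.

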7.2.4 SARS-CoV-2 Variants of Concern

Given the emergence of novel SARS-CoV-2 variants of concern, additional neutralization assays may be considered to evaluate effectiveness against variants of concern including the B.1.1.7, B.1.351, P.1, and B.1.617.2 (Delta) variant. Additionally, if any breakthrough infections are reported in patients in this study, whole genome sequencing will be performed in order to identify the viral lineage. Table 1 provides summary of study assessments.

Table 1: Schedule of Study Assessments for BOOST KIDNEY Protocol

Study Visit	Screening for Eligibility and Informed Consent	Baseline Study Assessment	Adverse Event Questionnaire	Serum SARS-CoV-2 Antibodies (Spike, RBD, NP) (5mL SST Tube)	SARS-CoV-2 Neutralizing Antibodies (5mL SST Tube)	PBMC (20mL Na Heparin blood) (n=50)	Vaccine Receipt and Participant Unblinding
Study Enrolment	X	X		X			
Prior to Booster					X	X	
Booster Vaccine Administration		X					
48 hours -14 days post-booster			X				

1 month			X	X	X	X	X
3 months				X			
6 months				X		X	
12 months				X			

7.3 Specimen Collection, Transportation, Bio-banking

For serum, blood will be collected in a single SST tube, and allowed to clot for 30 minutes and centrifuged for 10 minutes at 3000 x g at room temperature. Aliquots are made in 1 or 2 mL -80°C stable cryo-vials each with a volume of 300µL. Testing for three antigens (Anti-NP, Anti-Spike, and Anti-RBD) and surrogate SARS-CoV-2 pseudo-neutralization assay requires a minimum volume of 200µL. Tubes are labelled with the study code, participant ID, date of collection, and appropriate time point. Samples are transferred on dry-ice to the [name] Lab. A paper copy of list of samples sent is emailed using the template for data collection including labelled information in addition to vaccine type received and vaccination dates. Samples will not be collected if a participant has active COVID-19 as determined by Infection Control and Prevention but may resume when precautions have been discontinued. If a study participant has active COVID-19, clinical surplus if available at Sunnybrook may be processed into serum as part

of the Sunnybrook COVID-19 Biobank REB2109 and released to this study for serological analysis.

All study procedures will be in compliance with current Public Health guidelines for COVID-19 including the use of personal protective equipment, masking, and social distancing by all study personnel. If a study participant becomes infected with SARS-CoV-2, confirmed by RT-PCR during the course of the study, a study sample will not be collected from the participant with active COVID-19, but the participant will resume in the study once deemed safe by Public Health and their quarantine period is complete.

All infected patients will be referred for appropriate clinical care. Policies and procedures are already in place for in-center dialysis patients at each participating site to manage patients who have COVID-19 including ensuring appropriate isolation, droplet/contact precaution procedures, and informing Public Health authorities as well as local hospital Infection Prevention and Control. Non dialysis patients that become infected will also be referred for appropriate clinical follow-up and will be reported to Public Health Authorities per provincial mandates. All participating sites are experienced managing infected patients with established services to follow remotely and recommend admission when necessary. These services will be involved in each case to provide symptom assessment, develop an appropriate monitoring plan with regular severity assessments, and treatment plan for the patients.

For PBMC, 20 ml of heparinized blood will be separated into a mononuclear fraction by Ficoll-Paque or SepMate tube methodology. Blood samples will be separated into peripheral blood mononuclear cells and plasma within four hours of collection. Mononuclear cells will be viably frozen and plasma samples will be frozen for future use. Mononuclear cells will be frozen in 10% DMSO in alpha-MEM with 50% fetal bovine serum. Storage concentration is $1-10 \times 10^7$ cells/aliquot. Viable PBMC will be cryopreserved in vapor-phase liquid nitrogen.

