5.5.2 Blinding and Unblinding

Trial participants, study investigators, research team member, outcome assessors, and data analysts will be blinded to the intervention randomization. The individual dispensing and administering the vaccine will be aware of the vaccine being dispensed and administered but the patient will be blinded. Patients will be un-blinded to the vaccine they received following completing of adverse events following immunization reporting (30 days) and at that point will be provided with a vaccine receipt.

Un-blinding will only occur under exceptional circumstances where knowledge of the vaccine received is essential for further management of the study participant. Physicians are encouraged to discuss with the Qualified Investigator if un-blinding is necessary. If un-blinding is considered necessary, the Qualified Investigator will contact the randomization centre, who will do the code break as deemed necessary and communicate it directly to the attending physician. The Qualified Investigator will report all code breaks as they occur on the case report form.

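### The sample list in section 7.3 has an unrestricted vaccine-type field, which may disclose the randomised booster to the laboratory that measures the primary endpoint

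*Combined protocol and SAP*

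**What the plan says.** **Section 7.3 (specimens).** The tubes themselves do not show the vaccine: "Tubes are labelled with the study code, participant ID, date of collection, and appropriate time point". The next sentence covers shipment ("Samples are transferred on dry-ice to the" assay laboratory, whose name is removed). The one after it covers the paperwork, an emailed list of what was shipped, with this content: "including labelled information in addition to vaccine type received and vaccination dates". The recipient of the email is not named, and the text does not say which dose the vaccine type refers to.

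**Section 5.5.2 (blinding).** "Trial participants, study investigators, research team member, outcome assessors, and data analysts will be blinded to the intervention randomization". One exception is planned: "The individual dispensing and administering the vaccine will be aware of the vaccine being dispensed and administered but the patient will be blinded". Participants learn their booster at about one month: "Patients will be un-blinded to the vaccine they received following completing of adverse events following immunization reporting (30 days").

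**Section 10.5.1 (primary analysis).** "The primary outcome will be the proportion of patients who attain convalescent serum levels of Anti-RBD at 1 month (30 days) following third dose". The same section removes from the primary analysis anyone with new infection shown by a positive anti-NP test or RT-PCR.

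**Section 7.2.1 (assays).** A single laboratory does all serum testing, using a robotic quantitative ELISA calibrated against standards on every plate.

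**The concern.** The laboratory is in effect the outcome assessor for the primary endpoint. It produces the anti-RBD value that is compared with the convalescent median of 1.25, and the anti-NP value (positivity threshold 0.396) that can take a participant out of the primary analysis. Both cut-offs are in section 6.1.3.1. A document that travels with the samples and states the vaccine received, with no restriction, looks like a route by which allocation could reach the people section 5.5.2 means to blind. It also raises the question of how blinded site staff could fill in the field.

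What is at stake is how well the blinding of the primary measurement can be supported from the text. If the laboratory knows the arm, any judgement about a sample or a plate could be made with that knowledge, both for the endpoint and for who is analysed.

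**Working it through.** The plan gives no figure on this point, and the sample-size calculation is not in question. The check is a comparison of sections.

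1. **Does the list go to the laboratory?** Section 7.3 names no recipient. The sentence follows directly on the shipment of samples to the laboratory and describes a list of what was sent. The laboratory is the natural recipient, but this is an inference.

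2. **Does the field mean the booster?** The documents use the term both ways. Sections 4.1 and 5.5.1 use it for the first two doses, but with a qualifier (initial, baseline). Section 6.1.3 uses it without a qualifier for the study dose, when it says that the person giving the injection is not blinded. Section 7.3 has no qualifier. The literal reading includes the booster; the narrower reading is possible.

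3. **What would each reading reveal?** Randomisation is 1:1 within the initial-vaccine stratum. Knowing the initial vaccine therefore gives the stratum and says nothing about the arm. Knowing the booster gives the arm. Vaccination dates alone do not identify the arm, because every participant receives a booster.

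4. **Could booster type be known when each list is filled in?**
   - Samples before the booster: only the first two doses exist, so nothing about the booster can be entered.
   - 1-month sample (primary): Table 1 marks the blood draw, the adverse event questionnaire, and the vaccine receipt with participant unblinding all at this visit. Section 8.9.1 allows a 7-day window for the draw. The order within the visit is not fixed, so the booster can be known when the list is completed.
   - Samples at 3, 6 and 12 months: participants have been unblinded. A list with the booster on it would also link the arm to any 1-month result for the same participant ID that was not yet final.

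5. **Does anything in the plan close the gap?** Section 6.1.3 holds back the entry in the Ontario Renal Network tracker until after unblinding, so the plan guards against this kind of leak there. Section 7.3 has no matching safeguard. No section masks the booster on the list, and none exempts the laboratory from blinding.

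6. **Scale only.** Section 10.2 gives 300 participants and up to 10% loss. Assuming four equal groups, 300 × 0.90 / 4 = 67.5 per group. One result crossing 1.25 moves a group's response by 1 / 67.5 = 1.5 percentage points, and three move it by 3 / 67.5 = 4.4 points, against a target difference of 25 points. At the calculated 58 per group, one result is 1 / 58 = 1.7 points. The plan sets no quota by initial vaccine, so a smaller group would give each result more weight. This shows the weight of one result. It is not an estimate of bias, because nothing in the documents suggests that any result would move.

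**The case against.** The best case on the other side is that the field was meant for the first two doses. That reading makes sections 7.3 and 5.5.2 consistent. It also fits samples taken before the booster, if the same template serves them, and it explains how blinded staff could complete the form. This stands as a possible intention, but the text does not say it, and one qualifying phrase would be needed to make it so.

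Two further objections stand. Section 5.5.2 and Table 1 describe the unblinding of participants; they do not say that the staff who prepare samples learn the booster at that point. And the documents describe no discretionary step in the assay: repeat runs, plate acceptance and handling of out-of-range values are not mentioned, and a robotic, plate-calibrated ELISA leaves limited room for observer influence.

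A reader might infer more: that the laboratory will see allocation, that staff who fill in the list early must already be unblinded, or that the trial cannot claim blinded outcome assessment. The documents do not support these. The first rests on an unnamed recipient and an ambiguous term. The second holds only if the field means the booster, which is the open question. Against the third, section 5.5.2 expressly blinds outcome assessors and analysts; section 7.3 contains wording that, read literally, conflicts with that rule.

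**Conclusion.** The point holds as a conflict of wording that may break the blind. As written, section 7.3 asks for an item that may disclose the randomised booster to those measuring anti-RBD at 1 month and anti-NP, and section 5.5.2 does not allow for that. The timing makes disclosure feasible for the primary sample.

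The conclusion rests on two assumptions: that the list goes to the laboratory, and that the field is completed as literally worded. If it is meant for the initial series only, the arm is not revealed and only the wording is at fault. The size of any bias cannot be estimated from the documents and is probably limited by the automated, calibrated assay. The change is still worth making, because it protects both the primary measurement and the exclusion decision at almost no cost.

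**What to change.** - In section 7.3 and the shipment template, remove the vaccine-type field, or restrict it explicitly to the vaccine used for the first two doses.
- Otherwise send only study code, participant ID, collection date and time point, which is what the tubes already carry. Apply this at every time point, so that later lists do not reveal the arm for 1-month results that are still open.
- In section 5.5.2, state that laboratory staff and the staff who prepare samples are blinded to the booster.
- State that booster type is merged with the assay data only after the 1-month results are locked.

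The cost is a template change and a few sentences. No visit, sample, assay or sample-size figure changes. The documents give no reason why the laboratory needs the booster type to run the assay; if there is one, section 7.3 should state it and say how the blind is kept.
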